Appendix 1 Handling and Shipment of Bioanalytical Samples

1) Sample collection and processing procedures

Samples will be collected, processed, and stored according to procedures specified separately by the sponsor.

- Serum sodium concentration, serum potassium concentration, and serum osmolality
Blood will be taken using a serum separation tube, mixed by slowly turning upside-down several times, allowed to stand for at least 30 minutes at room temperature, and then centrifuged to obtain serum. The serum will be taken in a sample stock tube and stored refrigerated.
- Plasma AVP concentration
Blood will be taken using an EDTA-containing tube, mixed by slowly turning upside-down several times, and centrifuged at a refrigerated temperature to obtain plasma. The plasma will be taken in a sample stock tube and stored frozen.
- Plasma BNP concentration and plasma renin activity
Blood will be taken in an EDTA-containing tube from a subject who has remained at rest in a supine position, mixed by slowly turning upside-down several times, and centrifuged at a refrigerated temperature to obtain plasma. The plasma will be taken in a sample stock tube and stored frozen.
- Serum NT-proBNP concentration
Blood will be taken using a serum separation tube, mixed by slowly turning upside-down several times, allowed to stand for at least 30 minutes at room temperature, and then centrifuged to obtain serum. The serum will be taken in a sample stock tube and stored frozen.
- Serum troponin I concentration
Blood will be taken using a serum separation tube, mixed by slowly turning upside-down several times, allowed to stand for at least 30 minutes at room temperature, and then centrifuged to obtain serum. The serum will be taken in a sample stock tube and stored frozen.
- Urine sodium concentration, urine potassium concentration, and urine osmolality
The collected urine will be aliquoted into sample stock tubes and stored refrigerated.

2) Blood sample for DNA storage

Approximately 2 mL of blood will be taken in an EDTA-containing test tube. In principle, venous blood sampling by direct venipuncture or catheterization will be conducted, except in cases where the investigator or subinvestigator considers arterial blood sampling by catheterization to be preferable. The collected blood sample will be mixed by slowly turning upside-down several times, transferred to sample stock tube that is appropriately labeled, and then stored in a freezer set at below -20°C within 60 minutes after sampling. The status (collected/not collected), and the date and time of blood sampling will be recorded in the source document and the eCRF. The central laboratory will collect blood samples for DNA storage from each trial site and ship the samples to the DNA repository. The blood samples will be placed with an adequate amount of dry ice in an adiabatic container while being shipped. The DNA repository will store the blood samples in a freezer set at -70°C . After double coding the samples by assigning a new unique code to each sample, the DNA repository will extract the DNA and store the obtained DNA sample in a freezer set at -70°C . Upon the request of the sponsor, the DNA repository will discard the sample in such a state that the subject cannot be identified.

Appendix 2 Protocol Amendments/Administrative Changes

Amendment Number: 1

Issue Date: 18 Mar 2019

PURPOSES: Adding descriptions pertaining to clinical laboratory tests performed at each trial site using plasma samples, and correcting entry omissions and writing errors.

BACKGROUND: The use of plasma samples was considered appropriate in clinical laboratory tests at each trial site. Some entry omissions and writing errors were discovered in the protocol.

MODIFICATIONS TO PROTOCOL:

- Protocol Synopsis, Section 3.4.3
“Serum creatinine,” “serum sodium concentration,” and “serum potassium” were changed to “serum or plasma creatinine,” “serum or plasma sodium concentration,” and “serum or plasma potassium concentration,” respectively.
- Table 3.2.2-1 and Table 3.2.2-2
The following description was added: “^aIf serum sodium concentration measurement is difficult to perform at the trial site, plasma sodium concentrations will be used for the assessment.”
- Section 3.7
The following description was added: “If serum sodium concentration measurement is difficult to perform at the trial site, plasma sodium concentration may be measured. Either serum or plasma should be used consistently for measurement of sodium concentration in a given subject. However, serum sodium concentration will be measured at the central laboratory.”
- Table 3.7-1
Writing errors in the note were collected. The following description was added to Note d): “If serum sodium concentration measurement is difficult to perform at the trial site, plasma sodium concentration may be measured. Either serum or plasma samples should be used consistently for measurement of sodium concentration in a given subject. However, serum sodium concentration will be measured in the central laboratory.”
- Table 3.7.1.2-2 and Table 3.7.1.5-2

“Urine sampling for the measurement of urine sodium concentration and urine osmolality” was changed to “urine sampling for measurement of urine sodium concentration, urine potassium concentration, and urine osmolality.”

- Section 3.7.2.2

The following description was added: “If serum sodium concentration measurement is difficult to perform at the trial site, plasma sodium concentration may be measured. Either serum or plasma samples should be used consistently for measurement of sodium concentration in a given subject. However, serum sodium concentration will be measured in the central laboratory.”

- Table 3.7.2.2-1

“Serum electrolytes (sodium [Na], potassium [K], chloride [Cl], calcium [Ca])” was changed into “serum or plasma electrolytes (sodium [Na], potassium [K], chloride [Cl], calcium [Ca]).”

- Table 3.7.5.1.1-1

“24 hours before the start of IMP administration on Day 1” was changed into “23 to 25 hours before the start of IMP administration on Day 1.”

- Section 3.7.5.1.4

The following description was added: “If serum sodium concentration measurement is difficult to perform at the trial site, plasma sodium concentration may be measured. Either serum or plasma samples should be used consistently for measurement of sodium concentration in a given subject. However, serum sodium concentration will be measured in the central laboratory.”

- Section 3.8.3.2

“Serum sodium concentration” was changed into “serum or plasma sodium concentration.”

ADDITIONAL RISK TO THE SUBJECTS:

No additional risks will be imposed upon the subjects.

Amendment Number: 2

Issue Date: 26 Jun 2019

PURPOSES: Changing the protocol to enroll subjects who are not able to personally sign the ICF, but from whom verbal consent can be obtained in the presence of a witness; clarifying the definition of treatment duration; and, correcting writing errors.

BACKGROUND: It was found that some subjects are unable to personally sign the ICF due to physical or therapeutic reasons, even though they are able to verbally consent to participation in the trial; therefore, a procedure to enroll such subjects was added. The definition of treatment duration, which had been insufficiently documented was clarified. In addition, some errors were corrected.

MODIFICATIONS TO PROTOCOL:

- Throughout the protocol (Sections 3.3.2, 3.7.1, 3.7.4, 3.7.5.2.1, 3.9, 5.2, and 5.5)
The wording was changed so that subjects who express verbal consent can participate in the trial without obtaining written consent from these subjects (with this change, subjects may participate in the trial with verbal consent provided in the presence of a witness without providing written consent).
- Section 3.4.1
The wording was changed so that subjects who are able to consent but unable to sign the ICF for physical or therapeutic reasons can participate in the trial through the acquisition of verbal consent from these subjects in the presence of a witness. In the course of informed consent, the witness will sign and date the witness section of the ICF, and write the name of the subject, the reason(s) that the subject is not able to sign by him/herself, and the relationship between the subject and the witness in the margin of the ICF.
- Protocol Synopsis, Section 3.2.3
It was clarified that the participation of subjects in the trial would end when they become able to control fluid balance by oral fluid intake alone (the end of treatment period was clarified).
- Others: Errors were corrected.

ADDITIONAL RISK TO THE SUBJECTS:

No additional risks will be imposed upon the subjects.

Amendment Number: 3

Issue Date: 17 Apr 2020

PURPOSES: Addition of trial procedures and editing of descriptions in the protocol including the correction of errors

BACKGROUND: Trial procedures were added in consideration of ensuring the safety of subjects. The descriptions in the protocol were also edited (including the correction of errors.)

MODIFICATIONS TO PROTOCOL:

- Table 3.7-1
 - Item: The underlined parts were added.
Changed into “Serum sodium^d and potassium concentrations^d” in consideration of ensuring the safety of subjects.
 - Changed into “12-Lead ECG^k” in consideration of ensuring the safety of subjects.
 - Note d: The underlined parts were added.
Changed into “Serum sodium and potassium concentrations”
Changed into the following statement in consideration of ensuring the safety of subjects: “If serum sodium and potassium concentration measurement is difficult to perform at the trial site, plasma sodium and potassium concentrations may be measured. Either serum or plasma samples should be used consistently for measurement of sodium and potassium concentrations in a given subject. However, serum sodium and potassium concentrations will be measured in the central laboratory.”
 - Note e: The underlined parts were added.
Changed into the following statement in consideration of ensuring the safety of subjects: “Serum sodium concentration (local measurement), serum potassium concentration (local measurement), body weight, chest x-ray, and vital signs (blood pressure, pulse rate, and body temperature)”
 - Note k: An addition of the statement.
The following statement was added in consideration of ensuring the safety of subjects: “If the serum potassium is confirmed to exceed 5.5 mEq/L at the trial site or the central laboratory at any time point in the period with no specified 12-lead ECG, a 12-lead ECG will be performed as an unscheduled examination.”
- Sections 3.7, 3.7.1, 3.7.2.2 and 3.7.5.1.4
The statements indicating that “serum potassium concentration measurement is performed during the treatment period at the trial site” were added in consideration of ensuring the safety of subjects.

- Section 3.7.2.2 and 3.7.2.4

The statements indicating that “if the serum potassium is confirmed to exceed 5.5 mEq/L at the trial site or the central laboratory at any time point in the period with no specified 12-lead ECG,, a 12-lead ECG will be performed as an unscheduled examination” were added in consideration of ensuring the safety of subjects.

- Others: Errors were corrected.

ADDITIONAL RISK TO THE SUBJECTS:

No additional risks will be imposed upon the subjects.

Agreement

I, the undersigned principal investigator, have read and understand the protocol (including the Investigator's Brochure) and agree that it contains all the ethical, legal, and scientific information necessary to conduct this trial in accordance with the principles of Good Clinical Practices and as described herein and in the sponsor's (or designee's) Clinical Trial Agreement.

I will provide copies of the protocol to all physicians, nurses, and other professional personnel to whom I delegate trial responsibilities. I will discuss the protocol with these persons to ensure that they are sufficiently informed regarding the investigational new drug, OPC-61815, the concurrent medications, the efficacy and safety parameters, and the conduct of the trial in general. I am aware that this protocol must be approved by the Institutional Review Board (IRB) responsible for such matters in the clinical trial facility where OPC-61815 will be tested prior to commencement of this trial. I agree to adhere strictly to the attached protocol (unless amended in the manner set forth in the sponsor's Clinical Trial Agreement, at which time I agree to adhere strictly to the protocol, as amended).

## List of Abbreviations and Definition of Terms

Abbreviation	Definition
AE	Adverse event
ALT	Alanine aminotransferase
AST	Aspartate aminotransferase
AVP	Arginine vasopressin
BMI	Body mass index
BNP	Brain natriuretic peptide
CHF	Congestive heart failure
CRF	Case report form
ICD	Implantable cardioverter defibrillator
ICH	International Conference on Harmonisation
IMP	Investigational medicinal product
MedDRA	Medical Dictionary for Regulatory Activities
NYHA	New York Heart Association
PT	Preferred Term
QTc	QT corrected for heart rate
SOC	System Organ Class
TEAE	Treatment-emergent adverse event
ULN	Upper limit of normal

## 1 Introduction

This statistical analysis plan documents the details of the statistical analysis methodology to be applied in the protocol of Trial 263-102-00004.

## 2 Trial Objectives

To confirm the tolerability of intravenous administration of OPC-61815 at 8 or 16 mg once daily for a maximum of 5 days to congestive heart failure (CHF) patients with volume overload despite having received diuretics (injection) other than vasopressin antagonists and who have difficulty with or are incapable of oral intake.

## 3 Trial Design

### 3.1 Type/Design of Trial

This trial is a multi-center, uncontrolled, open-label trial to confirm the tolerability of intravenous administration of OPC-61815 at 8 or 16 mg once daily for a maximum of 5 days to CHF patients with volume overload despite having received diuretics (injection) other than vasopressin antagonists and who have difficulty with or are incapable of oral intake.

Subjects who meet all of the inclusion criteria and fall under none of the exclusion criteria at the screening examination will be advanced to the treatment period during which OPC-61815 will be intravenously administered at 8 or 16 mg once daily.

OPC-61815 treatment will start at 8 mg, and the investigator or subinvestigator will increase the dose to 16 mg on Day 2 or 3 after confirming that the subject meets the dose escalation criteria. The procedures for dose escalation decision are shown in the protocol [Section 3.2.2](#). The maximum treatment duration is 5 days; however, investigational medicinal product (IMP) treatment may be discontinued before Day 5 according to the rules specified in the protocol [Section 3.2.3](#). Concomitant use of loop diuretics will continue until the end of the treatment period.

The completion assessment will be conducted on Day 6 (or the day after the final IMP administration) and the follow-up assessment will be conducted at some time between 7 and 10 days after the final IMP administration. Subjects will be hospitalized from the time of informed consent to Day 6 (or the day after the final IMP administration).

### 3.2 Trial Treatments

The investigator or subinvestigator will administer OPC-61815 once daily as 1-hour infusion (55 to 70 minutes allowable) according to the IMP administration procedures

specified separately. OPC-61815 treatment will start with 8 mg, and eligibility for dose escalation will be assessed on Day 2 of the treatment period (and again on Day 3 of the treatment period, if applicable) according to the protocol [Section 3.2.2](#). If the dose escalation criteria are met, the dose will be increased to 16 mg; if the criteria are not met, administration will continue at 8 mg.

When adverse events (AEs) associated with the aquauretic effect of OPC-61815 including hypernatremia, dehydration, and thirst occur or worsen after the dose is increased to 16 mg and dose reduction is judged to be necessary by the investigator or subinvestigator, the dose will be returned to 8 mg. The dose may not be re-escalated to 16 mg once it has been reduced to 8 mg. The start time of administration on Day 2 and onward should coincide roughly ( $\pm 1$  hour, whenever possible) with the start time on Day 1.

### **3.3 Trial Population**

The trial population will comprise a total of 40 Japanese male and female CHF patients aged 20 to 85, inclusive, with volume overload despite having received injection diuretics other than vasopressin antagonists and who have difficulty with or are incapable of oral intake and who are capable of being hospitalized from the time of informed consent until the end of the treatment period.

### **3.4 Handling of Time Points**

Case report form (CRF) Visit values at each time point (time points from baseline in the screening, treatment, and follow-up periods as specified in the protocol Table 3.7.1) will be used in summaries (but values at the time of discontinuation will not be used in summaries). Unscheduled Visit values will not be used.

According to the rules specified in the protocol [Section 3.2.3](#), for the completion assessment of subjects who have completed treatment after a treatment period of shorter than 5 days, the CRF Visit will be set to correspond with the day of assessment for the analysis visit. Concerning interval urine samples, the daily urine volume will be calculated by summing all the interval urine volumes that constitute the daily urine volume for that day. If the interval urine sample is the last one for that day, the corresponding interval will be set as the analysis interval. The same rules also apply to fluid intake and urine electrolyte excretion. Other variables specified in the corresponding CRF Visit to be measured multiple times will be set to precede IMP administration.

Baseline and final administration time point for each variable are defined as follows.

Table 3.4-1 Handling of Time Points		
Variable	Baseline	Final Administration Time Point
Clinical laboratory value	Before IMP administration on Day 1	Day after final IMP administration
Vital signs	Before IMP administration on Day 1 (Screening values will be used if the values at screening are measured on Day 1 but not measured prior to the IMP administration on that day.)	Day after final IMP administration
12-lead ECG	Before IMP administration on Day 1	Day after final IMP administration
Daily urine volume, daily fluid intake, daily fluid balance	Within 24 hours before IMP administration on Day 1	-
Serum sodium concentration, serum potassium concentration, serum osmolality	Before IMP administration on Day 1	-
Daily urine sodium excretion, daily urine potassium excretion	Within 24 hours before IMP administration on Day 1	-
Urine osmolality	Within 24 hours before IMP administration on Day 1	-
Biomarkers (plasma AVP concentration, plasma renin activity, plasma brain natriuretic peptide [BNP] concentration, serum N-terminal pro-brain natriuretic peptide [NT-proBNP] concentration, and serum troponin I concentration)	Before IMP administration on Day 1	Day after final IMP administration
Body weight	Before IMP administration on Day 1 (Screening values will be used if the values at screening are measured on Day 1 but not measured prior to the IMP administration on that day.)	Day after final IMP administration
Congestive symptoms (lower limb edema, jugular venous distension, hepatomegaly, pulmonary rales, cardiac third sound)	Screening	Day after final IMP administration
Pulmonary congestion, cardiothoracic ratio	Screening	Day after final IMP administration
Respiratory rate, paroxysmal nocturnal dyspnea, orthopnea	Screening	Day after final IMP administration
Subject-assessed dyspnea	Screening	Day after final IMP administration
NYHA classification	Screening	Day after final IMP administration

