3.2.3 Treatment Duration

The maximum duration of treatment will be 5 days; however, IMP treatment may be ended at a treatment period of shorter than 5 days at the discretion of the investigator or subinvestigator, if either of the following criteria is met:

- All congestive symptoms are resolved and no further improvement in volume overload is necessary.
- The subject becomes capable of fluid management by oral intake alone.

[Rationale for the treatment duration]

The maximum treatment duration in this trial is 5 days, which is the same as that in the phase 3 confirmatory trial (Trial 263-102-00003).

If all congestive symptoms disappear and further improvement in volume overload is judged unnecessary by the investigator or subinvestigator, IMP treatment will be ended because no additional diuretic treatment is required. In addition, if fluid control by oral intake alone is attained during the treatment period, IMP treatment will be ended because the subject is judged to have recovered from difficulty in or incapability of oral intake.

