3.7.1.7 Treatment Period (Completion Assessment on Day 6 or Withdrawal Assessment)

The investigator or subinvestigator will conduct the completion assessment at a feasible time on Day 6 as described below. If IMP administration is discontinued before Day 5, the same assessment as the completion assessment on Day 6 will be conducted as the withdrawal assessment on the day after the final IMP administration, whenever possible.

1) At the end of urine collection

- Urine sodium concentration (central measurement)
- Urine osmolality (central measurement)
- Urine potassium concentration (central measurement)

2) At a feasible time

- Serum sodium concentration (local measurement, central measurement)
- Serum potassium concentration (local measurement, central measurement)
- Serum osmolality (central measurement)
- Biomarkers (central measurement)
- Body weight

- Dyspnea (respiratory rate, paroxysmal nocturnal dyspnea, orthopnea, and subject-assessed dyspnea)
- Congestive symptoms (lower limb edema, hepatomegaly, jugular venous distension, pulmonary rales, and cardiac third sound)
- Chest x-ray (cardiothoracic ratio and pulmonary congestion)
- Clinical laboratory tests (central measurement)
- Physical examination
- Vital signs (blood pressure, pulse rate, and body temperature)
- 12-Lead ECG
- NYHA classification
- Adverse Events
- Concomitant medications and therapies

3.7.1.8 Follow-up After End of the Treatment Period (7 to 10 Days After the Final IMP Administration)

The investigator or subinvestigator will conduct the following examinations and tests within 7 to 10 days after the final IMP administration. If the subject has already been discharged from the trial site, the follow-up may be conducted on an outpatient basis.

- Serum sodium concentration (central measurement)
- Serum potassium concentration (central measurement)
- Body weight
- Congestive symptoms (lower limb edema, hepatomegaly, jugular venous distension, pulmonary rales, and cardiac third sound)
- Clinical laboratory tests (central measurement)
- Physical examination
- Vital signs (blood pressure, pulse rate, and body temperature)
- Adverse Events
- Urine pregnancy test (WOCBP only)
- Concomitant medications and therapies

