3.8.3.2 Documenting Reasons for Treatment Discontinuation

A subject may discontinue participation in the trial at any time, and the investigator or subinvestigator may discontinue a subject's participation in the trial if medically necessary. Subjects who fall under any of the following must be withdrawn from the trial. If a subject discontinues treatment, a single reason for the discontinuation (the main reason) will be recorded in the eCRF.

1) Reasons related to AE:

- Subject decides to discontinue because of annoyance or discomfort due to a non-serious AE which is not otherwise determined to be an undue hazard
- AST or ALT value is ≥ 3 times the upper limit of normal (ULN).
- Serum or plasma sodium concentration measured at the trial site or the central laboratory increases by ≥ 12 mEq/L from immediately predose within 24 hours after start of the IMP administration.
- The serum or plasma sodium concentration measured at the trial site or the central laboratory is ≥ 155 mEq/L during the treatment period.
- The onset of drug-induced hypersensitivity is suspected.

- Any severe AESI (feeling abnormal, feeling hot, erythema, hyperhidrosis, pruritus, rash, urticaria, nausea, epigastric discomfort, or dyspnea) occurs.
- Continuing IMP places the subject at undue risk as determined by the investigator or subinvestigator (eg, a safety concern that is possibly, probably, or likely related to IMP).
 - Serious adverse event
 - Other potentially IMP-related safety concerns or AEs

- 2) Withdrawal of informed consent by the subject (when it is confirmed to be unrelated to AEs)
- 3) Protocol deviations (other than poor compliance with the IMP administration rules)
 - Deviations related to the inclusion or exclusion criteria
 - Deviations related to prohibited concomitant medications
- 4) Judgment by the investigator or subinvestigator (for the reasons other than an AE)
- 5) Death
- 6) Lost to follow-up
- 7) Pregnancy (see [Section 5.5](#))
- 8) Technical problems (eg, malfunctions of medical devices)
- 9) Premature termination of the entire or part of the trial by the sponsor

If the subject discontinues IMP due to an AE, the investigator, subinvestigator, or other trial personnel, will make every effort to follow the event until it has resolved or stabilized, or until the subject is lost to follow-up or has died.

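### SAP 3.4 keeps the day-after-final-dose values of early completers in the by-visit summaries but drops those of discontinued subjects, and the pharmacodynamic sodium, potassium and osmolality tables have no other time point at which to recover them

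*SAP*

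**What the plan says.** SAP 3.4 uses scheduled CRF visit values at each time point, "but values at the time of discontinuation will not be used in summaries", and adds: "Unscheduled Visit values will not be used". For subjects who complete in fewer than 5 days it takes the opposite course: "the CRF Visit will be set to correspond with the day of assessment for the analysis visit".

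Protocol 3.2.3 gives two grounds for early completion: "All congestive symptoms are resolved and no further improvement in volume overload is necessary", or "The subject becomes capable of fluid management by oral intake alone". Protocol 3.8.3.2 lists the reasons for discontinuation. Among them is "Serum or plasma sodium concentration measured at the trial site or the central laboratory increases by" ≥12 "mEq/L from immediately predose within 24 hours after start of the IMP administration", and another is a sodium of ≥155 mEq/L during treatment. SAP 7.1 counts the two groups separately, as completed and discontinued.

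The assessment itself does not differ. Under Protocol 3.7.1.7, when dosing stops before Day 5 the Day 6 assessment "will be conducted as the withdrawal assessment on the day after the final IMP administration", whenever possible.

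SAP Table 3.4-1 also defines a final administration time point, the day after the last dose, for laboratory values, vital signs, ECG, biomarkers, weight, congestion, dyspnea and NYHA class. SAP 5.4 fills gaps there with the last available value. For serum sodium, potassium and osmolality as pharmacodynamic variables the table shows a dash, and SAP 11.2 summarises them by visit only.

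**The concern.** Two subjects may both receive their last dose on Day 3 and both be assessed on Day 4. If the first stopped because congestion had cleared, the Day 4 values enter the Day 4 summary. If the second stopped because sodium rose too far, they do not. Whether a value counts depends largely on how the subject fared.

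Protocol 2.1 gives hypernatremia and dehydration as the reason this population needs its own tolerability trial. After Day 1, on days without escalation, Protocol Table 3.7-1 schedules sodium only before dosing, so the next-day sample is the only scheduled sodium reading that follows that dose. For a subject withdrawn at that point, this is the value excluded. The SAP gives no reason for the exclusion. Protocol section 7 contains no such rule, and SAP section 14 does not list it among the changes to the planned analyses.

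**Working it through.** **Is there a stated figure to reproduce?** Not for this rule. The only computed figure in the plan is the sample-size statement, and it reproduces: 1 − 0.95^40 = 0.871 and 1 − 0.96^40 = 0.805, against the stated 87% and 80%.

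**Step 1. Where does a discontinued subject's day-after value go?**

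| Variable | By-visit summary | Final administration time point |
|---|---|---|
| Weight, vital signs, congestion | Excluded (SAP 3.4) | Defined and summarised (SAP 8.3.1, 8.3.2, 9.4) |
| Sodium, potassium as laboratory tests | Excluded | Defined and summarised (SAP 9.3; shift table CT-10.3.2) |
| Sodium, potassium as pharmacodynamic variables | Excluded | None (dash in Table 3.4-1; SAP 11.2) |
| Serum osmolality | Excluded | None; it is not in the laboratory panel (Protocol Table 3.7.2.2-1) |

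Sodium and potassium have a second route through the laboratory tables. Osmolality has none.

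**Step 2. What stays in.** All scheduled values up to the last dosing day stay. On Day 1 and the escalation day these include the 4-hour and 8-hour samples (Protocol 3.7.1.2 and 3.7.1.5). The loss is one assessment per discontinued subject.

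**Step 3. Size, as an illustration.** The documents give neither a sodium mean nor a discontinuation rate for this trial. Assume 40 subjects would have a value at one visit, and that d of them were withdrawn for sodium and are all assessed at that visit. If the excluded values average x and the rest average m, then

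shift in the mean when the values are restored = [(40 − d)·m + d·x]/40 − m = d·(x − m)/40.

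The values of x are the protocol's own withdrawal thresholds; the values of m are assumptions.

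| d | Change scale: x = +12, m = 4 to 0 | Level scale: x = 155, m = 143 to 140 |
|---|---|---|
| 1 | 0.2 to 0.3 | 0.3 to 0.375 |
| 2 | 0.4 to 0.6 | 0.6 to 0.75 |
| 3 | 0.6 to 0.9 | 0.9 to 1.125 |
| 4 | 0.8 to 1.2 | 1.2 to 1.5 |

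All entries are in mEq/L. The overall range for 1 to 4 subjects is 0.2 to 1.5. The effect on the maximum, which the SAP's descriptive statistics include, can be much larger: a value of 155 would be missing from that visit's row.

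SAP 9 and 11 repeat the analyses by escalation status, so smaller denominators apply. In an assumed group of 10, one value of 155 against 140 shifts the mean by 15/10 = 1.5 mEq/L.

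**Step 4. Is d = 1 to 4 a sensible range?** Protocol 1.2.2 reports phase 2 stopping for adverse events in 2 of 48 subjects on OPC-61815 and 3 of 12 on the tablet. Scaled to 40, the first is 40 × 2/48 = 1.7 and the pooled figure is 40 × 5/60 = 3.3. None of the five reasons given was sodium, so this indicates stopping for any adverse event, not for sodium.

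**The case against.** The strongest reply is that little is really lost. Weight, congestion, dyspnea and NYHA class have their confidence intervals at the final administration time point, where discontinued subjects are included on the ordinary reading. Vital signs and laboratory sodium are summarised there too. Adverse events, including those leading to discontinuation, are tabulated for every treated subject (SAP 9.2). Sodium threshold events are counted per subject (SAP 9.3), and individual values appear in listings. No primary or secondary outcome is set, so no formal conclusion rests on a by-visit mean.

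Most of this stands and limits the point. A reader might infer that the profiles lose the subjects who did not tolerate the drug, or that weight and response are made to look better. The documents do not support either. One value is lost, not the subject. Discontinuation also covers consent withdrawal, protocol deviations and technical problems, which are not intolerance. A subject withdrawn for high sodium after a strong aquaresis may have lost a good deal of weight, so omitting that weight could understate response. Nor need the day-after sodium be the peak: a triggering value may be a retained 4-hour or 8-hour sample, and infusion solution is checked and adjusted on every dosing day.

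Two things remain. The final time point does not exist for the pharmacodynamic sodium, potassium and osmolality tables. And the exclusion in SAP 3.4 is unqualified: read literally, it also bars the withdrawal value from the final time point, where SAP 5.4 would then substitute an earlier one. The ordinary reading is the more natural, but the text does not settle it.

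**Conclusion.** The point holds in a limited form. SAP 3.4 treats the same day-after assessment differently for two kinds of early stopper who are separated largely by outcome, and gives no reason. By-visit summaries lose one value per discontinued subject. The consequence is clearest for pharmacodynamic serum sodium and potassium, and above all for osmolality, which has no second route back into a summary.

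The size is illustrative: about 0.2 to 1.5 mEq/L in one visit's mean sodium for 1 to 4 of 40 subjects, with a possible loss of the maximum. This assumes that the withdrawals are for sodium, fall at one visit and have day-after values at the protocol's thresholds. Fewer sodium withdrawals, or withdrawals spread over several days, would make the shift at any one visit smaller; smaller denominators would make it larger. No direction of bias is claimed for weight or response. For the variables that have a final administration time point, the loss is confined to the by-visit rows, provided the exclusion does not extend to that time point.

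**What to change.** Replace the parenthesis in SAP 3.4 with: *Values from the withdrawal assessment made the day following the last dose are assigned to the analysis visit of the day of assessment, as for early completers.* State that these values also count at the final administration time point. In Table 3.4-1, define that time point for serum sodium, potassium and osmolality as pharmacodynamic variables, and add the matching summary to SAP 11.2; this also brings the pharmacodynamic and laboratory rows for sodium and potassium into line.

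The cost is small: a sentence or two, one table row and one added summary, using the mapping already needed for early completers. No new data are collected. By-visit means may look slightly less favourable.
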